#### 9.4.7.3 Safety Follow-up Period

Patients who complete 3 weeks of randomized treatment are eligible to enter the RAP-MD-04 maintenance study. If they do not enter RAP-MD-04, they should enter the safety follow-up period. Patients who discontinue the study prematurely should enter the safety follow-up period. No IP is administered during the safety follow-up period and patients' background ADT may be modified as deemed appropriate by the Investigator.

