#### 9.5.2.1 Adverse Events

An AE is any untoward medical occurrence in a patient or clinical investigation patient administered a pharmaceutical product and which does not necessarily have to have a causal relationship with this treatment. An AE can therefore be any unfavorable and unintended sign (including an abnormal laboratory finding, for example), symptom, or disease temporally associated with the use of a medicinal product, whether or not considered related to the medicinal product (ICH-E2A).

For the purpose of the study center's data collection responsibilities, any untoward event that was reported from the time the patient signed the ICF until 30 days after the final protocol-defined study visit or the last known dose of IP (if the final visit does not occur) is to be considered an AE.

Examples of AEs are as follows:

- Changes in the general condition of the patient
- Subjective symptoms offered by or elicited from the patient
- Objective signs observed by the Investigator or other study center personnel
- All diseases that occur after signing informed consent, including any change in severity or frequency of pre-existing disease
- All clinically relevant abnormalities in laboratory values or clinically relevant physical findings that occur during the study schedule

Please note that medical procedures scheduled prior to consenting, but occurring during the study should not be captured as AEs, but should be listed in the medical history if related to a pre-existing condition.

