### 9.5.2.1.4 Reporting Adverse Events and Serious Adverse Events

At each visit, patients are to be queried regarding any AEs or SAEs that have occurred since the previous visit. Patients will be asked to volunteer information with a nonleading question such as, "How do you feel since your last visit?" Study center personnel will record all pertinent information in the patient's eCRF.

All AEs must be recorded on the appropriate AE reporting page of the patient's eCRF whether or not they are considered causally related to the IP.

For every AE, the Investigator must:

- Provide an assessment of the seriousness of the event (ie, is it an SAE?), as well as the severity and casual relationship
- Document all actions taken with regard to the IP
- Detail any other treatment measures taken for the AE
- Document the outcome of the AE

In addition, patients are to be reminded, as described in the ICF and in accordance with Section 9.5.2.1, to notify study center personnel of any AEs occurring during the 30-day poststudy period. Any AEs reported by the patient (or patient representative) during this period are to be recorded in original source documents. AEs are also to be recorded in the eCRF if at least one of the following conditions is met: 1) the event meets the criteria for an SAE (see Sections 9.5.2.1.3 and 9.5.2.1.4), and/or 2) the event is judged by the Investigator to be potentially causally related to IP.

Any AEs that are ongoing at the time of the final protocol-defined study visit will be followed until the condition returns to prestudy status, has resolved or stabilized, or can be explained as being unrelated to the IP. If a follow-up visit is deemed necessary for appropriate safety surveillance, it will take place within 30 days of the final protocol-defined study visit.

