# 9.7.6.1 Adverse Events

AEs will be coded by system organ class and preferred term using the *Medical Dictionary for Regulatory Activities*.

An AE (classified by preferred term) will be considered a treatment-emergent adverse event (TEAE) if it was not present before the first dose of IP or was present before the date of the first dose of IP and increased in severity after the first dose of IP. An AE that becomes serious after the date of first dose of IP will also be considered as a TEAE. If more than 1 AE is reported before the first dose of IP and coded to the same preferred term, the AE with the greatest severity will be used for comparison with the AEs occurring during the double-blind treatment period that were also coded to that preferred term. An AE that occurs more than 30 days after the date of the last dose of IP will not be considered as a TEAE.

The number and percentage of patients reporting TEAEs in each treatment group will be tabulated by system organ class and preferred term and further categorized by severity and causal relationship to the IP. If more than 1 AE is coded to the same preferred term for the same patient, the patient will be counted only once for that preferred term using the greatest severity and strictest causality for the summarization by severity and causal relationship.

A serious adverse event (SAE) that occurred between the date of the first dose of IP and 30 days after the date of the last dose of IP, inclusive, will be considered a treatment-emergent SAE (TESAE). The number and percentage of patients who have TESAEs will be summarized by preferred term and treatment group. In addition, the incidence of TESAEs that lead to death will be summarized separately by preferred term for each treatment group.

Overall summaries of AEs will be provided on a per-patient basis for categories of all TEAEs, treatment-related TEAEs, TESAEs, and TEAEs leading to study discontinuation.

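### The 30-day TEAE and TESAE window does not separate events after a first RAP-MD-04 dose from events under RAP-MD-02 treatment (minor)

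*Protocol*

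**What the plan says.** Protocol Section 9.7.6.1 sets the end of the TEAE window: "An AE that occurs more than 30 days after the date of the last dose of IP will not be considered as a TEAE". A serious event is a TESAE if it is one "that occurred between the date of the first dose of IP and 30 days after the date of the last dose of IP, inclusive". Both kinds are attributed to the randomized group. For TESAEs the text reads "The number and percentage of patients who have TESAEs will be summarized by preferred term and treatment group", and deaths get their own table: "the incidence of TESAEs that lead to death will be summarized separately by preferred term for each treatment group".

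Section 9.4.7.3 allows rollover: "Patients who complete 3 weeks of randomized treatment are eligible to enter the RAP-MD-04 maintenance study". Sections 9.1.2 and 9.5.6 say the same.

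AE collection runs, under Section 9.5.2.1, "until 30 days after the final protocol-defined study visit or the last known dose of IP", the latter applying if the final visit does not take place. For the poststudy period, Section 9.5.2.1.4 limits what enters the eCRF: "AEs are also to be recorded in the eCRF if at least one of the following conditions is met". The conditions are that the event is serious, or that "the event is judged by the Investigator to be potentially causally related to IP".

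None of these sections makes an exception for patients who enter RAP-MD-04. The readable text treats those patients differently only in Sections 9.1, 9.1.2, 9.1.3, 9.4.7.3 and 9.5.6, and only in that they do not need the 1-week safety follow-up.

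**The concern.** A 30-day post-dose window suits a patient who leaves the trial untreated. It suits less well a patient who can start a second study one week after the last dose. For that patient most of the window may lie inside RAP-MD-04. Under the rule as written, an SAE after a RAP-MD-04 dose but within 30 days of the last RAP-MD-02 dose is a TESAE of the RAP-MD-02 arm.

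Safety is one of the study's objectives (Section 8.0), and the study is meant to support a regulatory application (Section 7.0). The tables affected are those for TESAEs, fatal TESAEs and treatment-related TEAEs. Where events are few, even one or two placed without distinction could change how a by-arm table reads.

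**Working it through.** **Inputs**
- Doses at Visits 2, 5 and 8 (Section 9.4.7).
- Treatment days 7 days apart, with visits allowed 2 days either side except those 24 hours apart (Section 9.1.2).
- Last double-blind visit on Day 21 (Section 9.7.9).
- Window of last dose + 30 days (Section 9.7.6.1). IP is taken here to mean the RAP-MD-02 product. The section does not say so, and the window would run longer if the RAP-MD-04 product also counted.

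**1. Reproduce the plan's visit day.** Visit 2 = Day 0; Visit 5 = 0 + 7 = Day 7; Visit 8 = 7 + 7 = Day 14; Visit 11 = 14 + 7 = Day 21. This matches Section 9.7.9.

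**2. Nominal overlap.** Window end = 14 + 30 = Day 44. Days after possible RAP-MD-04 entry = 44 − 21 = 23, which is 23/30 = 77% of the post-dose window.

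**3. Visit windows.**
- Visit 11 timed from the Visit 8 dose: 30 − (7 + 2) = 21 to 30 − (7 − 2) = 25 days.
- Both visits shifting around dates fixed from baseline: (12 + 30) − 23 = 19 to (16 + 30) − 19 = 27 days. The 27-day end puts Visits 8 and 11 only three days apart, so it is an extreme.

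**4. Start of RAP-MD-04 dosing.** The document does not give it. If it is assumed to lie between Day 21 and Day 28, the overlap with dosing is 44 − 21 = 23 down to 44 − 28 = 16 days.

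**5. Last dose at Visit 5 (Visit 8 injection missed).** (7 + 30) − 21 = 16 days. Section 9.4.7.3 does not settle whether such a patient counts as having completed treatment, so this case is only illustrative.

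**6. Does the recording rule close the gap?** For a rollover patient the final visit appears to be Visit 11, so collection runs to 21 + 30 = Day 51. Counted from the last dose it would run to Day 44. Either way it covers the whole window, so it does not close the gap. It does narrow the events concerned: after the final visit only SAEs and AEs judged potentially IP-related reach the eCRF. Other poststudy AEs stay in source documents and cannot enter the tables.

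**7. How many patients could be concerned?** Section 9.7.9 expects about 630 patients and reports dropout below 5% at the time of Amendment 2. If that held to the end, more than 630 × 0.95 ≈ 598 could be eligible to roll over. The number who do so is not stated.

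**The case against.** The strongest reply is that Section 9.7.6.1 gives a conventional definition and is merely silent on a sub-case. Rules for patients who enter an extension often sit in the SAP or in dataset specifications. The public text also has gaps: any introduction to the safety analyses before Section 9.7.6.1 and the visit-by-visit descriptions in Section 9.5.6 cannot be read. This stands in part. A rule may exist elsewhere, which is why the point is minor. But the protocol fixes the window itself, and any rule elsewhere would need to agree with it.

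Second, a nonserious poststudy AE enters the eCRF only if judged potentially related to IP, so counting it under the RAP-MD-02 arm follows the investigator's judgement. This largely stands. That judgement is harder to make once another study's dose has been given, but the main concern is SAEs.

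Third, a reader might infer that the window should simply stop at rollover. The documents do not support that. It would remove SAEs and deaths within 30 days of a randomized dose from the tables because of something that happened after randomization. One common 30-day window for all arms is the more inclusive choice and should stay.

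A reader might also infer that the safety tables will be biased, for instance toward no difference because placebo patients later receive active drug. The protocol does not give the RAP-MD-04 treatments, the date of the first dose there or the rollover rate by arm, so neither the fact nor the direction of bias can be asserted.

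**Conclusion.** The point holds as a minor one. Read literally, Section 9.7.6.1 assigns to the RAP-MD-02 arm any SAE or potentially IP-related AE that arises after a RAP-MD-04 dose but within 30 days of the last RAP-MD-02 dose, without marking it. The overlap per rollover patient is nominally up to 23 of 30 post-dose days, or 21 to 25 with the visit window counted from Visit 8. It shortens day for day if RAP-MD-04 dosing starts later.

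This rests on three assumptions: that RAP-MD-04 dosing begins before about Day 44, that events are entered in the RAP-MD-02 eCRF as Section 9.5.2.1.4 directs, and that no rule elsewhere separates them. No count of misplaced events can be derived. Efficacy, type I error and sample size are not affected.

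**What to change.** In Section 9.7.6.1, keep the 30-day window and add the following for patients who enter RAP-MD-04:
- Present the TEAE, TESAE and fatal-TESAE counts by treatment group, split into events before and events on or after the first RAP-MD-04 dose.
- Base the between-group comparison of RAP-MD-02 treatment on the events before that dose.
- List the later events by RAP-MD-02 arm.
- Show the number of rollovers per arm beside the tables.

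The full 30-day counts remain on display, so no SAE or death is lost. State that IP here means the RAP-MD-02 product, and align the wording with any rule in the SAP.

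The cost is one extra date item (first RAP-MD-04 dose) and one extra split or listing. The downside is shorter follow-up in the comparison for rollover patients: 21 − 14 = 7 post-dose days if RAP-MD-04 dosing starts at Visit 11, or 28 − 14 = 14 if it starts on Day 28, against 30 for other patients. If rollover differs between arms, so does that follow-up. The rollover counts and the retained 30-day tables are there to show this.

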## 9.7.8 Interim Analysis

At the time of preparation for Protocol Amendment 2, a blinded interim analysis was performed as part of data quality review as the study was progressing. In this review, it was observed that the SD for the primary and secondary endpoints were substantially lower than the originally assumed values for sample size calculations. The observed SDs in the blinded reviews of this study and other ongoing acute studies at the same time (RAP-MD-02 and RAP-MD-03) were taken into consideration for revising the estimate of the sample size as proposed in the next section (Section 9.7.9 Determination of Sample Size).

### 9.7.9 Determination of Sample Size

The originally proposed primary efficacy variable is the change from baseline in the MADRS total score at 1 day after the first dose of treatment. The study was planned to randomize 1050 patients assuming SD of 10 points, which provides 99% power to detect a difference of 3.25 points in MADRS total score between at least 1 of the 2 rapastinel dose groups and placebo at a 2-sided significance level of 0.05.

While the study was ongoing, the primary efficacy variable was revised to be the change from baseline in MADRS score at the last visit, Day 21, as recommended by the FDA, EMA, and PDMA, and included in Amendment 2 of the protocol. At the same time of Amendment 2, a blinded data review was conducted for Studies RAP-MD-01, RAP-MD-02, and RAP-MD-03. The pooled SD for the 3 studies were 7.4, 8.0, and 8.7, respectively, all smaller than the originally assumed 10 points. Sample size was recalculated using 8.7 as the common SD. The calculation used MMRM model with simulations; it also assumed correlation of 0.5 between the repeated measures and an overall dropout rate of 15%. To have 90% power, the total sample size required is 540 patients. However, the study had already enrolled more than 590 patients with less than 5% of overall dropout rate, surpassing the re-estimated sample size of 540 patients. The study enrollment will be halted as soon as operationally feasible. The final sample size expected is approximately 630 patients (210 patients per treatment group).

# 9.7.10 Computer Methods

Statistical analyses will be performed using version 9.3 (or newer) of SAS.

#### 9.8 DATA AND SAFETY MONITORING BOARD

The study will be conducted under the supervision of an independent DSMB to be chartered to review safety data at predetermined points during the study. The DSMB may also decide to meet and review safety data at other timepoints should it be deemed necessary. The DSMB is responsible for the ongoing review of safety data in the clinical study and for making recommendations concerning the continuation, modification, and termination of the study (FDA Guidance for Clinical Trial Sponsors: Establishment and Operation of Clinical Trial Data Monitoring Committees, March 2006).

All analyses that are required to support the DSMB will be performed by an independent unblinded statistician not otherwise involved in the study. Details of the DSMB membership, meeting schedule, and data review and analysis will be documented in the DSMB Charter.

# 9.9 CHANGES IN THE CONDUCT OF THE STUDY OR PLANNED ANALYSES

Any amendment to this protocol will be provided to the Investigator in writing by the Sponsor. No protocol amendment may be implemented (with the exceptions noted below) before it has been approved by the IRB, and the signature page, signed by the Investigator, has been received by the Sponsor. If the protocol is amended to eliminate or reduce the risk to patients, the amendment may be implemented before IRB review and approval. However, the IRB must be informed in writing of such an amendment, and approval must be obtained within reasonable time limits.

#### 9.10 PROTOCOL DEVIATIONS

A protocol deviation is any change, divergence, or departure from the study design or procedures that is under the Investigator's responsibility and oversight (as defined by regulations) without prior written IRB approval or favorable opinion of an appropriate amendment and that does not have a major impact on the patient's rights, safety, or well-being, or on the integrity and authenticity of the study data. Deviations may include, but are not limited to, departure from inclusion/exclusion criteria, dosing, duration of treatment, failure to perform the required assessments at specified timepoints, scheduling of visits not in accordance with specifications, or patient safety. Deviating from the protocol is permitted only if absolutely necessary for the safety or clinical management of the patients and must immediately be reported to the Sponsor.

A *significant important protocol deviation* is a form of protocol deviation that has a major impact on the patient's rights, safety, or well-being, or on the integrity and authenticity of the study data. Important protocol deviations must be reported to the Sponsor within 24 hours, if possible. The IRB must be notified within the time period dictated by the IRB associated with this study.

# 10.0 STUDY SPONSORSHIP

This study is sponsored by Naurex, Inc, an affiliate of Allergan, plc.

## 10.1 STUDY TERMINATION

The Sponsor reserves the right to terminate the study in its entirety or at a specific study center before study completion.

## 10.2 REPORTING AND PUBLICATION

All data generated in this study are the property of the Sponsor. An integrated clinical and statistical report will be prepared at the completion of the study.

Publication of the results by the Investigator will be subject to mutual agreement between the Investigator and the Sponsor and will follow the Sponsor's Standard Operating Procedure on publications.

# 11.0 INVESTIGATOR OBLIGATIONS

#### 11.1 DOCUMENTATION

The Investigator must provide the following to the Sponsor before the start of the study:

- A completed and signed Form FDA 1572. If, during the course of the study, any changes are made that are not reflected on Form FDA 1572, a new Form FDA 1572 must be completed and returned to the Sponsor for submission to the FDA
- A fully executed contract
- The curricula vitae for the Investigator and all subinvestigators listed on Form FDA 1572, including a copy of each physician's license
- A copy of the original IRB approval for conducting the study. If the study is ongoing, renewals must be submitted at yearly intervals. All subsequent modifications must be submitted and approved by the IRB, as stated in Section 5.1.
- A copy of the IRB-approved ICF
- A copy of the HIPAA authorization form, or other local privacy applicable forms
- A list of the IRB members or the US Department of Health and Human Services general assurance number
- A copy of the laboratory certifications and reference ranges
- The Investigator's Statement page in this protocol, signed and dated by the Investigator
- Financial disclosure agreement, completed and signed by the Investigator and all subinvestigators listed on Form FDA 1572. The Investigator and all subinvestigators will provide an updated financial disclosure agreement to the Sponsor 1 year after the completion of the study.

#### 11.2 PERFORMANCE

The Investigator must demonstrate reasonable efforts to obtain qualified patients for the study.

#### 11.3 USE OF INVESTIGATIONAL MATERIALS

The Investigator will acknowledge that the IP supplies are investigational and as such must be used strictly in accordance with the protocol and only under the supervision of the Investigator or subinvestigators listed on Form FDA 1572. The IP must be stored in a secured place and must be locked. At study initiation, a representative from the Sponsor will inventory the IP at the study center. The Investigator must maintain adequate records documenting the receipt and disposition of all study supplies. The Sponsor will supply forms on which to record the date the IP was received and a dispensing record in which to record each patient's use. All unused IP must be returned to the Sponsor.

#### 11.4 CASE REPORT FORMS

All patient data relating to the study will be recorded on eCRFs to be provided by the Sponsor through the EDC system. The Investigator is responsible for verifying that all data entries in the eCRFs are accurate and correct by electronically signing the completed eCRF casebook submitted to the Sponsor. The Investigator must maintain and retain accurate documentation that supports the information entered into the EDC system for source document verification and possible regulatory inspection.

#### 11.5 RETENTION AND REVIEW OF RECORDS

Records and documents pertaining to the conduct of this study, including eCRFs, source documents, consent forms, regulatory documents, clinical laboratory results, calibration logs, or reports (including, but not limited to, all local and central laboratory results and ECG reports), and medication inventory records in all formats (including, but not limited to, written, electronic, magnetic, and optical records, and scans, x-rays, and ECGs) must be retained by the Investigator for a period of at least 15 years after study completion unless local regulations or institutional policies require a longer retention period or otherwise notified in writing by the Sponsor.

No study records shall be destroyed without notifying the Sponsor and providing the Sponsor the opportunity to arrange long-term storage for such study records or authorizing in writing the destruction of records after the required retention period.

The Investigator must permit access to any documentation relating to the study upon request of the Sponsor or applicable regulatory authorities. If the Investigator for the study retires, relocates, or for other reasons withdraws from the responsibility of keeping the study records, custody must be transferred to a suitable alternate custodian employee of the institution or to a suitably qualified and responsible third party. The Sponsor must be notified in writing of the name and address of the new custodian in advance of the transfer.

